**STATEMENT OF COMPLIANCE FOR NON DRUG OR DEVICE CLINICAL TRIALS**

This document is a protocol for a clinical research study. The study will be conducted in compliance with all stipulations of this protocol, the conditions of ethics committee approval, the NHMRC National Statement on Ethical Conduct in Human Research (as updated) and the Handbook for Good Clinical Research Practice (GCP). The Therapeutic Goods Act has adopted ICH Guideline for Good Clinical Practice.

**1. GENERAL INFORMATION**

**1.1 Protocol title**

Rapid Syllable Transition Treatment for Adults

**1.3 Name of the study funder**

No external funding

**1.6 Trial registration - Trial identifier and registry name**

The Australian New Zealand Clinical Trials Registry (ANZCTR), (reg number to be provided)

**2. SYNOPSIS**

TITLE	Rapid Syllable Transition Treatment for Adults
PRIMARY HYPOTHESIS	That Rapid Syllable Transition Treatment (ReST) will be effective in improving speech intelligibility of adults with apraxia.
DESIGN	Single case experimental design – multiple baselines within participants
BLINDING/MASKING	Single blind As a behavioural intervention trial, the treating clinicians and participants cannot be blinded to allocated group or intervention.
OUTCOMES	The primary outcome Speech intelligibility in single words Secondary outcomes 
 
1. Participant satisfaction with the intervention
 
2. Speech accuracy
 
3. Sentence complexity and length in speech
 

STUDY DURATION	Estimated study duration from initial enrolment until completion of data analyses is 21 months
INTERVENTION/S	Rapid Syllable Transition Treatment (ReST)
NUMBER OF PARTICIPANTS	6 in 1 group
POPULATION	Sample Size : n=6 Gender : Male and female Age : Adults aged over 18 Demographic group : N/A Diagnosis : Apraxia of speech from any cause
SELECTION AND ENROLMENT	Inclusion criteria: 
 
1) Aged over 18 years
 
2) Diagnosis of apraxia
 
3) No diagnosis of intellectual disability, dementia or other significant disorder which effects speech production.
 
4) Normal or adjusted-to-normal hearing (screened) and vision (self-report).
 

### **3. RATIONALE / BACKGROUND**

#### **3.1 Background**

Apraxia of speech is a brain-based neurological speech disorder that causes people to have difficulty making a plan for how to say words and sentences despite no problems in the function of their muscles or peripheral nerves (ASHA, 2007). This inability to plan can make their speech slow, halting, staccato or slurred. Apraxia has a number of causes including genetics, disease or injury. Apraxia can occur from birth or can be acquired later in life. It is not associated with reduced intellectual capacity or understanding of spoken or written language although these can co-occur.

Rapid Syllable Transition (ReST; McCabe et al., 2017) treatment is an evidence-based speech pathology treatment for apraxia of speech which has been shown to be effective with children and young people (e.g., Murray et al., 2015; McCabe et al., 2023) when provided at least twice per week (Thomas et al., 2014; 2023). ReST involves the use of multisyllabic pseudowords to improve the ability to transition rapidly and fluently from one sound/syllable to the next, and control of the rhythm in the form of relative emphasis, or stress, placed on each syllable within a word (McCabe et al., 2017).

ReST treatment teaches patients to say nonsense words and gets them to copy a model of someone saying the nonsense word correctly. In doing so, the person with apraxia is required to practice planning to speak, thus it is believed that the treatment addresses their difficulty directly. Details about ReST treatment and video examples of the treatment with children are available at [www.rest.sydney.edu.au](http://www.rest.sydney.edu.au).

#### **3.2 Rationale for Study**

Although ReST was designed for those with childhood apraxia of speech and tested on children aged 4-14, it has been used widely in clinical practice with adults (McCabe et al., 2020). This study is an examination of an existing treatment which is being used clinically with this population (adults) and will use within-participant comparisons (single case experimental design) to report the effects of a usual clinical practice. Should ReST be an effective intervention, the results of this study will provide data to power a sample size calculation for a larger study.

### **4. AIMS / OBJECTIVES / HYPOTHESES**

#### Aim:

The study aims to investigate if Rapid Syllable Transition Treatment (ReST) is effective in improving speech intelligibility in adults with apraxia of speech.

#### Hypothesis:

1. ReST will be effective in improving speech intelligibility in adults

**6. STUDY DESIGN**

**6.1 Type of Study**

This is a single blind multiple baselines within participant study

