**PROCEDURES**

1. Following consent, participants will be assessed by a qualified speech pathologist (one of the investigators) using standard speech pathology tools. This assessment will take no more than one hour. Tasks will include saying words and sentences, reading a passage, having a hearing screening and completing an oral movement assessment (OMA) which includes tasks such as stick out your tongue; lick your lips, alternate between a kiss and a smile and say /a/ for as long as you can (forms attached). The assessment will be audio and video recorded.
2. Following standard ReST protocol, one of the investigators will then create a list of words for each participant consisting of 20 treatment words, 10 control (untreated) words, 10 untreated generalisation sentences and 30 generalisation words. This list of 70 items is called the Probe list and participants will be asked to say it on a number of occasions described below.

3. Prior to treatment, each participant will be asked to say the 70 item probe list on five separate days (max 30 minutes per session) and these will be recorded as the baseline performance.
4. Treatment will be provided by a trained speech pathology student for one hour twice per week for six weeks at a mutually convenient time. Treatment consists of learning to say the nonsense words. No home practice is required. Treatment may be face-to-face in the on-campus speech pathology clinic or it may be on Zoom. This choice will be up to participant preference.
5. Immediately prior to the fifth and ninth sessions, participants will be asked to say the 70 word probe list and this will be recorded. 20 minutes on each occasion.
6. Immediately following the final (twelfth) session, participants will be asked to say the 70 word probe list and this will be recorded. 20 minutes.
7. Participants will return to the clinic one day, one week, two weeks and four weeks after finishing treatment and say the 70 word probe list on each occasion. On the one week and two week post treatment occasions, they will be asked to say the list twice. Each visit will take approximately 30-40 minutes.
8. Four weeks after completion of the treatment, participants will also repeat several of the tasks completed in the initial assessment (step 1) and say the probe list for the final time (60 minutes total)
9. Following the four week appointment a short report on their individual performance in treatment will be sent to each participant for their own records.

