#### 6.4.5 Randomisation and Blinding Processes

##### Randomization

There is no randomization in this study.

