### **6.14 Statistical analyses**

Data analysis will utilize repeated measures visual analysis. When a treatment effect is evident visually, statistical analysis within participant, across treatment phase (I.e. baseline, treatment, follow-up) will be calculated using Helmert Planned orthogonal contrasts.

Effect sizes within participant will be calculated using  $d^2$ , as this measure is appropriate for single case data (Beeson & Robey, 2006).

If there is any attrition, an intention-to-treat analysis will be conducted.

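### The design is labelled multiple baselines but has no staggered start, and the stated phase contrast gives the untreated control words no role, so drift in the probe scores could pass for a treatment effect

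*Protocol*

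**What the plan says.** The synopsis describes a single case experimental design with "multiple baselines within participants", and section 6.1 repeats the label: "This is a single blind multiple baselines within participant study". Section 6.4.5 adds: "There is no randomization in this study".

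The procedures in section 6.2 set out the schedule:

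- **Items:** each participant's list has "20 treatment words, 10 control (untreated) words, 10 untreated generalisation sentences and 30 generalisation words".
- **Baseline:** "each participant will be asked to say the 70 item probe list on five separate days".
- **Treatment:** one block, "one hour twice per week for six weeks at a mutually convenient time", that is 12 sessions.
- **Later probes:** the whole list is probed before sessions 5 and 9, after session 12, and at four follow-up visits, two of which have two readings.

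Section 6.14 begins with visual analysis. If an effect is visible, "statistical analysis within participant, across treatment phase (I.e. baseline, treatment, follow-up) will be calculated using Helmert Planned orthogonal contrasts". A within-participant effect size follows.

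In section 6.5 the primary outcome is a standardised intelligibility test. The probe list feeds only a secondary outcome, phonemes correct.

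**The concern.** A multiple-baseline design controls for time by staggering. Treatment reaches different behaviours, item sets or participants at different moments, and the inference rests on each series changing when its own treatment starts. Without a stagger, what remains is a baseline-treatment-follow-up series, in which anything that improves with time or repetition looks like treatment.

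Upward drift is plausible on the protocol's own terms. The same list is said many times. Apraxia of any cause is eligible, with no limit on time since onset and no stability requirement. Section 7.1.2 accepts that attending therapy may help in itself.

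The untreated control words could separate these influences from treatment, but neither section 6.5 nor section 6.14 assigns them a role. Two things are at stake: how far a positive probe result can be attributed to ReST, and the size of the probe effect if it is used to plan the larger study mentioned in sections 3.2 and 6.3.

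**Working it through.** The protocol gives no alpha, power, effect size or SD, so there is no stated figure to reproduce.

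**1. Is there a stagger?** Items: 20 + 10 + 10 + 30 = 70, as stated. Only the 20 treatment words are treated, and they start together; the other 50 are never treated. Baseline length is the same for all participants. Table 2 allots visits 3 to 8 (six visits) to baseline probes where step 3 says five days. Those entries need reconciling, but neither creates a later start for anyone or anything.

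**2. Number of readings.** Baseline 5; during treatment 2; end of treatment 1; follow-up 1 + 2 + 2 + 1 = 6. Total 14. The protocol does not say whether the end-of-treatment reading belongs to treatment or follow-up, so both splits are shown: 5/2/7 and 5/3/6.

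**3. The contrast.** The first Helmert contrast is L = (mean_T + mean_F)/2 − mean_B, with SE = s × √(1/5 + 1/(4n_T) + 1/(4n_F)) and 14 − 3 = 11 residual df.

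- 5/2/7: √(0.2 + 0.125 + 0.0357) = 0.601 s
- 5/3/6: √(0.2 + 0.0833 + 0.0417) = 0.570 s

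**4. What drift does to it.** Assume no treatment effect and a linear drift of D session SDs over the 13 steps from first to last probe. Numbering probes 0 to 13:

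- 5/2/7: phase means fall at 2, 5.5 and 10, so L = (7.75 − 2) × D/13. For D = 2, L = 0.88 SD.
- 5/3/6: phase means fall at 2, 6 and 10.5, so L = (8.25 − 2) × D/13. For D = 2, L = 0.96 SD.

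Simulated rejection rates (two-sided 0.05, independent normal errors with SD 1, visual step not modelled):

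| Drift D | Phase only, 5/2/7 | Phase only, 5/3/6 | Treated minus control, drift fully shared |
|---|---|---|---|
| 0 | 5% | 5% | 5% |
| 1 | 10% | 12% | 5% |
| 2 | 25% | 32% | 5% |
| 3 | 45% | 58% | 5% |

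The last column is 5% by construction, because identical drift is subtracted. For D = 2, if control words drift half as much as treated words the rate is about 7%; if they do not drift at all it is 12% (5/2/7) or 14% (5/3/6).

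**5. Would the baseline reveal the drift?** With drift of 1 to 3 SDs, a slope test on the five baseline points finds a significant rise in only about 3% to 8% of series.

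**6. Cost of the difference score.** With 10 control and 20 treated words and no shared session noise, control variance is taken as twice the treated variance, so the SE ratio is √(1 + 2) = 1.73. For a true step effect with the 5/3/6 split:

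- 2 SD: noncentrality 2/0.570 = 3.51, power about 89%; after dividing by 1.73 it is 2.03, power about 46%.
- 1.5 SD: power falls from about 67% to about 28%.

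Shared session noise would make the loss smaller.

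**The case against.** The strongest reply has four parts.

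- **Visual analysis comes first.** The contrast is run only if an effect is visible, so the percentages above are not the error rates of the planned procedure. This stands as a limit on the numbers. However, the visual step has no written rule, a steady rise can look like an effect, and the test that follows is still phase-only.
- **The control words are not excluded.** Section 6.14 does not say which series are plotted or tested, and detail may sit in a SAP. A reader might infer that the plan discards the control words; the text does not show that. What it does fix is a comparison across phases within participant, with no comparison between item sets.
- **Scorers are blinded to recording order.** This protects against rater expectation. It does nothing about real change in speech through practice or recovery.
- **This is a six-person early study meant to inform a sample size.** That lowers the severity. It does not remove the point, because the stated hypothesis is one of effectiveness and an effect estimate inflated by drift would be a poor basis for planning.

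A reader might also infer that a treated-minus-control contrast would rescue the main hypothesis. It would not. The primary intelligibility test has no control items. In the written schedule it is taken at initial assessment, and only several unnamed initial tasks are repeated, once, at four weeks.

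**Conclusion.** The point holds and should be fixed. The label claims a source of control that the procedures do not provide, and the stated contrast cannot separate treatment from drift on the probe outcome.

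How large the distortion would be is unknown. The range of 10% to 58% rests on assumed linear drift of 1 to 3 session SDs, independent errors and no visual screening. It shows that the test is exposed to drift and does not predict this trial's error rate. A reader might conclude that drift will be counted as a treatment effect; the documents support only that it could be.

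For the primary outcome, any change is an uncontrolled pre-post difference and cannot establish effectiveness by itself. This is not a fatal flaw: the control-word data are already planned, and the repair for the probe outcome is a matter of wording.

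**What to change.** - **Section 6.14:** for phonemes correct, base any claim of a treatment effect on the phase-by-item-set contrast, per participant: change from baseline in treated words minus change in the 10 control words. Plot both series in the visual analysis. Report the phase-only contrast as descriptive. State which phase the end-of-treatment probe belongs to.
- **Section 6.1 and synopsis:** replace the multiple-baselines label with a baseline-treatment-follow-up design with untreated control items.
- **Sections 6.5 and 6.14:** state that the intelligibility test has no control items and no repeated baseline in the written schedule, so its change is an uncontrolled pre-post difference.

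**Cost:** no new data and no extra visits. The contrast is noisier, with the SE up to about 1.7 times as large and the power loss shown above in the worst case. It is conservative if treatment generalises to the control words, and protects fully only if both sets drift alike. Staggering baseline lengths at random across participants would earn the label, but it changes procedures and adds visits, so it is optional.

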**6.2 Schedule of Events/ Treatment Phases**

Table 1 study timeline (subject to approval timeframe)

Events and time						
Feb 2024	March 2024	July 2024	Feb 2025	July 2025	Oct 2025	Dec 2025
Ethics, clinical trial registration;	Rolling recruitment, assessment & therapy					Close trial
Train student clinicians		Train student clinicians	Train student clinicians (if required)	Train student clinicians (if required)	Final recruitment	

All patient facing procedures form part of speech pathology usual care except extra data collection listed below in items 3, 7, and 8 where usual procedures are repeated more frequently than would occur in usual care.

Table 2: Flowchart of the participation in the trial for each participant (n=6)

Weeks	0	Visits 1-2	Visits 3-8	Visits 9-22	Visits 8 & 12	Visit 23	Visit 24	Visit 25	Visit 26
	Consent	Assessment	Pre-treatment probe data collection	Treatment	Within treatment probe data collection	1 day follow up	1 week follow up	2 week follow up	4 week follow up

**PROCEDURES**

1. Following consent, participants will be assessed by a qualified speech pathologist (one of the investigators) using standard speech pathology tools. This assessment will take no more than one hour. Tasks will include saying words and sentences, reading a passage, having a hearing screening and completing an oral movement assessment (OMA) which includes tasks such as stick out your tongue; lick your lips, alternate between a kiss and a smile and say /a/ for as long as you can (forms attached). The assessment will be audio and video recorded.
2. Following standard ReST protocol, one of the investigators will then create a list of words for each participant consisting of 20 treatment words, 10 control (untreated) words, 10 untreated generalisation sentences and 30 generalisation words. This list of 70 items is called the Probe list and participants will be asked to say it on a number of occasions described below.

3. Prior to treatment, each participant will be asked to say the 70 item probe list on five separate days (max 30 minutes per session) and these will be recorded as the baseline performance.
4. Treatment will be provided by a trained speech pathology student for one hour twice per week for six weeks at a mutually convenient time. Treatment consists of learning to say the nonsense words. No home practice is required. Treatment may be face-to-face in the on-campus speech pathology clinic or it may be on Zoom. This choice will be up to participant preference.
5. Immediately prior to the fifth and ninth sessions, participants will be asked to say the 70 word probe list and this will be recorded. 20 minutes on each occasion.
6. Immediately following the final (twelfth) session, participants will be asked to say the 70 word probe list and this will be recorded. 20 minutes.
7. Participants will return to the clinic one day, one week, two weeks and four weeks after finishing treatment and say the 70 word probe list on each occasion. On the one week and two week post treatment occasions, they will be asked to say the list twice. Each visit will take approximately 30-40 minutes.
8. Four weeks after completion of the treatment, participants will also repeat several of the tasks completed in the initial assessment (step 1) and say the probe list for the final time (60 minutes total)
9. Following the four week appointment a short report on their individual performance in treatment will be sent to each participant for their own records.

NB: Clinic here refers to online or face-to-face clinical services

### **6.3 Population / Sample size including power calculation**

#### Sample size:

The sample size will be 6 participants

Sample size calculation: This is a phase 1 study to acquire data for a sample size calculation

### **6.4 Participant Enrolment and Randomisation**

#### **6.4.1 Recruitment**

Participants will be recruited from The University of Sydney speech pathology clinic and speech-language pathology services in Australia and other English-speaking countries. The study will be advertised on the ReST website, social media (Instagram, Facebook, LinkedIn and Twitter/X), and on Speech Pathology Australia e-newsletters and website. The study flyer will direct potential participants who are interested to contact the chief investigator [name] or follow a link to the research website ([www.rest.sydney.edu.au](http://www.rest.sydney.edu.au)).

When participants contact the chief investigator, they will be informed about the purpose of the study and provided with the Participant Information Sheet. An opportunity to ask questions will be provided.

#### **6.4.2 Inclusion and Exclusion Criteria**

##### **INCLUSION CRITERIA**

Participants will be adults aged over 18 with apraxia of speech. Participants will have English as their primary language and have functional literacy in English. Participants will have adequate hearing and vision to participate in the treatment (glasses and hearing aids are fine). Participants who choose to participate by telehealth will need to have their own laptop or tablet device and access to the internet. Participants will be competent to independently provide consent (i.e. no one with a

guardianship order).

#### EXCLUSION CRITERIA

Participants will not have another serious genetic or developmental diagnosis which affects speech or cognition such as Down Syndrome or Cerebral Palsy. Participants will not have another serious acquired neurological disorder which affects speech or cognition such as Parkinsons disease or Alzheimers.

#### 6.4.3 Informed consent process

The informed consent process involves the following:

Interested persons will contact the chief investigator or follow links from a social media site or email to the ReST research webpage. They will be provided with the Participant Information Sheet and the Participant Consent Form. Participants will be encouraged to ask questions about the research and the risks and benefits of participation.

Potential participants will be informed that their participation is completely voluntary. They are free to decline to attend the study, and also free to withdraw from the study at any time. This will have no implications on their relationship with the research team or the University of Sydney.

Consent will be recorded in (1) a RedCAP version of the participant consent form or (2) a written consent form which will then be scanned and added to RedCAP.

#### 6.4.4. Eligibility and pretreatment assessment

Following consent, participants will complete the following assessment tasks to (1) measure their performance prior to treatment (2) provide information for therapy planning (3) provide adequate description of each participant's communication skills and (4) to ensure they meet the inclusion and exclusion criteria. All tasks are standard speech pathology practice:

1. Complete a case history questionnaire
2. Hearing screening
3. Oral musculature evaluation – an examination of the structure and function of the muscles of speech
4. Apraxia Battery for Adults 2nd edition (speech and oral apraxia evaluation)
5. Apraxia Severity Rating Scale (speech tasks)
6. Assessment of Intelligibility in Dysarthric Speech (speech tasks)
7. PALPA – nonword repetition, sentence comprehension and reading letter names subtests
8. Picture description – the participant will be asked to verbally describe a picture.

